8 STUDY ENDPOINTS

The primary study endpoint is measuring early recovery of postoperative course by calculating early return of bowel motion (passing flatus and/or stool on which postoperative day), presence or absence of nausea and/or vomiting, presence or absence of chest symptoms (cough, sputum

PROTOCOL TITLE: Does increased mobility assessed with 3D motion tracking technology lead to early post-operative recovery among patients undergoing oncologic surgeries

and ability of using incentive spirometry), early discharge from the hospital and 30 days surgical related complications and readmissions.

The secondary study endpoint is measuring the range of joint movement in upper and lower joints of body, using the 3D motion tracking system (Xsens), to identify the minimum required level of mobility for better early postoperative course recovery.

A few other secondary endpoints concluded from the post experiment questionnaire include: assessing encouraged walking in the hospital setting subjectively improves their exercise habit outside of the hospital, how was the application of the sensors in a hospital setting as this is the first study to do so, and to assess the subjective impact of complications on quality of life.

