9 PROCEDURES INVOLVED

This is a prospective randomized controlled trial comparing the early postoperative course of patients who undergo inpatient oncological procedures after assessment of their baseline physical activity before the surgery, using validated questionnaires in the clinic, to have a homogenized sample for the study. Participants will be randomized to the control arm (40 participants) and intervention group (40 participants). Control group participants will be asked to walk one to two laps around the ward twice per day, on the first day after the surgery following the usual clinical practice at Roswell Park Comprehensive Cancer Center-urology department (RPCCC). Their movement will be tracked with 3D motion tracking system (Xsens). The intervention arm participants will be asked to walk for minimum 30 minutes per day and their movement also will be tracked with Xsens. In both arms the patients will be asked to mobilize (walk out of the bed) on first day post-surgery under supervision and assistant of attending nurse in the floor if their clinical situation allowed. If patient cannot complete the walking tasks, they will be excluded from the study and they will be replaced by recruiting other patients.

Xsens is a wireless technology that makes use of sensors. The sensors are applied in a non-invasive manner and do not require the suit to be applied. There are various configurations of the sensors that can be utilized. The minimum number of sensors needed is 7. They are applied by using Velcro bands. The entire set-up takes about 5-10 minutes.

The study duration is 24 months or until target accrual is reached. In both arms their mobility will be tracked till they discharged from the hospital. In both arms we will assess the symptoms and signs of gastro-intestinal complications (nausea, vomiting, abdominal pain, passing flatus or stool) and chest symptoms (coughing, sputum, utilizing incentive spirometry) until they are discharged from the hospital. We will continue to follow them for 30 days post discharge to note any complications or readmission.

Patients at standard follow ups, 2 weeks, 6 weeks, 3 months or over the phone will complete a short post study questionnaire (Appendix B). The last three questions are taken from Woodfield et al., who assessed postoperative problems from the perspective of the patient on the identification of complications after surgery (11).

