16 STATISTICAL PLAN

Demographics: Subject demographic and clinical characteristics will be reported by group using the appropriate descriptive statistics and graphical summaries. Comparisons will be made between groups using the Mann-Whitney U or Chi-square tests, as appropriate.

Randomization: Subjects will be randomized to the control and intervention groups in a 1:1 fashion using a permutation block design (block sizes = 4). The randomization list will be developed by the study statistician.

Primary Analysis: The primary objective is to evaluate changes in mobility between the control (standard of care) and intervention (additional activity) groups. The primary outcomes are measures of mobility (i.e. range of movement), which are treated as continuous measures and will be summarized by group and time-point using the mean, median, and standard deviation. The measures of mobility will each be modeled as a function of treatment group, time post-surgery, their two-way interaction, and random subject effects using a linear mixed model. Within each group, the effect of time on the mean will be evaluated using tests about the appropriate contrasts of model estimates. The effect of the two groups on the time-mobility relationship will be evaluated using an F-test about the interaction term. All model assumptions will be evaluated graphically and transformations will be applied as necessary.

Secondary Analyses: The secondary objective is to evaluate the impact on post-surgical complications. The complication status (present/absent) and grades will be summarized by group and compared using Fisher's exact test or the chi-square test, as appropriate.

PROTOCOL TITLE: Does increased mobility assessed with 3D motion tracking technology lead to early post-operative recovery among patients undergoing oncologic surgeries

The association between complication status and changes in measures of mobility may be evaluated using logistic regression models.

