Sample Size Determination: The power calculations are based on the primary analysis, which compares the changes in measures of mobility between the two groups. Since the form of the models is unknown beforehand, a simplified and conservative power calculation is based on comparing the mean change (baseline to discharge) in a given mobility measure between groups using a two-sided, two-sample t-test. With a sample size of n=40 per group, we have 80% power (at $\alpha = 0.05$) to detect a difference of at least 0.63 standard deviations. Such a moderate effect size would be considered clinically relevant.

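### Bowel return is dated by flatus and/or stool in whole days, with no rule for which event counts: precision can be gained cheaply, and no bias is shown

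*Combined protocol and SAP*

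**What the plan says.** Section 8 states that "The primary study endpoint is measuring early recovery of postoperative course" and lists several components. The first is bowel return, by "calculating early return of bowel motion (passing flatus and/or stool on which postoperative day". The unit is therefore the postoperative day, and either milestone or both may count.

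Section 9 returns to the topic in its list of gastro-intestinal symptoms and signs: "nausea, vomiting, abdominal pain, passing flatus or stool". These are assessed "until they are discharged from the hospital". Neither section says which event fixes the date, who records it, how often patients are asked, whether a clock time is taken, or what happens when a patient goes home before the event.

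Section 16 names different outcomes: "The primary outcomes are measures of mobility (i.e. range of movement), which are treated as continuous measures". Its secondary analyses concern complications: "The complication status (present/absent) and grades will be summarized by group". It names no analysis of bowel return.

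**The concern.** Flatus and stool are different milestones and may be many hours apart. Under the present wording, two people following the protocol faithfully could give the same patient different days, one from first flatus and the other from first stool. That adds variation unrelated to the walking programme. Counting in whole calendar days discards further information, because operations end at different times of day and a plausible benefit may be shorter than a day.

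At stake is how well a component that Section 8 calls primary can separate two arms of 40. The choice also cannot be undone: a single unlabelled day cannot later be split into its two milestones.

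**Working it through.** **The plan's own figure.** Section 16 states "With a sample size of n=40 per group, we have 80% power" at two-sided α = 0.05 for 0.63 SD, "using a two-sided, two-sample t-test". The exact noncentral t gives 79.5% power at 0.63 SD and a detectable difference of 0.634 SD, so the figure reproduces. It concerns mobility; the documents give no power for bowel return. I use 40 per arm and 0.63 SD below only as a common yardstick.

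**Inputs.** From the documents: 40 per arm, 1:1 allocation, α = 0.05, postoperative-day unit. Assumed, because the documents give nothing: distribution of times, SDs, flatus-to-stool gap, end-of-surgery times and mixing shares.

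**Step 1: whole days against hours, one milestone.** Times are normal with SD s hours and a true difference of 0.63 s. Surgery ends at clock hour c, uniform from 08:00 to 20:00, and postoperative day = floor((c + t)/24). The calendar cut adds a variance of about 24²/12 = 48 h² and the spread of c adds 12²/12 = 12 h². The standardised difference therefore becomes

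d = 0.63 s / √(s² + 60).

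For s = 12: 7.56/√204 = 0.529. For s = 24: 15.12/√636 = 0.600. For s = 48: 30.24/√2364 = 0.622. The simulated columns are t-tests over 6,000 runs.

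| Assumed SD | Power, hours (simulated) | Power, days (simulated) | Power, days (formula) | Loss, points (simulated) |
|---|---|---|---|---|
| 12 h | 79% | 64% | 65% | about 15 |
| 18 h | 80% | 72% | 72% | about 8 |
| 24 h | 80% | 75% | 75% | about 5 |
| 36 h | 79% | 77% | 78% | about 2 |
| 48 h | 80% | 79% | 78% | about 1 |

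A Mann-Whitney test shows the same pattern (78% against 72% at SD 24 h). At SD 24 h the mean difference is 15.1 h on either scale. With no true effect, day recording gives a type I error of 5.0% to 5.7%. The loss is one of precision, not validity.

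**Step 2: which milestone counts.** Assumed: flatus mean 60 h, SD 24 h, stool about 36 h later, effect 0.63 × 24 = 15.1 h, all in hours so that rounding plays no part.

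| What the intervention shifts | First of the two | Stool alone | Either at random, 50/50 |
|---|---|---|---|
| Both milestones | 80% | 62% | 54% |
| Stool only | 5% | 62% | 19% |
| Flatus only | 79% | 5% | 16% |

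A first-event rule behaves almost exactly as flatus alone. It loses nothing when both milestones move and detects nothing when only stool moves. Unregulated mixing is costly in every row in which flatus moves, and is well below stool alone when only stool moves.

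A second model points the same way: gamma times with mean 54 h and SD 18 h, a 12 h benefit, a Mann-Whitney test, and stool lagging by a mean of 24 h. Power over repeated simulations was 86–89% in hours, 80–83% in whole days, 69–71% with 20% of patients dated by stool, and 54–58% with 50%. Clock times wrong by up to 4 h cost almost nothing.

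**Step 3: no true effect.** An equal 50/50 mix in both arms gives about 4% false positives, so no inflation. If the share dated by flatus is 40% in one arm and 60% in the other, the spurious difference is 0.2 × 36 ≈ 7 h and false positives are 17%. At 30% against 70% it is 0.4 × 36 ≈ 14 to 15 h and 53%. In the second model, stool dating of 30% against 10% gives 0.2 × 24 = 4.8 h (0.2 day) and 12%. All these splits are assumed.

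**The case against.** The strongest reply is that the Section 8 wording reads naturally as the first day on which either event occurs. On that reading there is no mixing, and only the rounding loss of Step 1 remains. Eligibility covers any oncologic surgery, so times may spread widely; at an SD of 36 to 48 h that loss is only 1 to 2 points. The text also does not prevent the two events from being recorded separately. And the power figures belong to a test that Section 16 does not contain. All of this stands, and it limits the point to a clarification with a modest gain. It does not supply the missing rule.

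A reader might go further and infer that the measure is biased, or that staff who know the arm choose the milestone. The documents do not support either. Day recording and an equal mix leave type I error near 5%. No section says who dates the event or that anyone has discretion over it. It is true that the arms receive visibly different walking instructions and that no blinding or independent assessor is described, so recording that differs by arm cannot be excluded. That is an exposure, not a finding.

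The Section 9 wording is also weak evidence of a conflict, since it lists signs to be assessed and does not define the endpoint.

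**Conclusion.** The point holds as a cheap improvement to an under-defined component of the Section 8 primary endpoint. Under the first-event reading, whole-day recording costs about 1 to 15 power points as the assumed SD falls from 48 h to 12 h, with no bias. If milestones are mixed, the loss is larger: 80% to 54% with a 50/50 mix when both milestones shift. False positives rise only when the mix differs by arm, and the sizes shown (12% to 53%) rest wholly on assumed splits.

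It would be wrong to read this as a loss of power in the trial's planned primary analysis. Section 16 makes mobility primary and powers the trial on it. The disagreement between Sections 8 and 16 over what is primary is a larger and separate matter.

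**What to change.** - Record date and approximate clock time of first flatus and of first stool as two separate fields, in the same way in both arms.
- In Section 8, define bowel return as hours from end of surgery to the first of the two, and use the same wording in Section 9.
- Report time to first stool separately, because a first-event measure mostly reflects flatus.
- In Section 16, name a rank-based or time-to-event comparison, with discharge before the event treated as censored. A plain Mann-Whitney test has no place for censored times, so a log-rank comparison is the simpler choice if any occur. Early discharge may itself signal good recovery, so the number censored should be shown by arm.

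The cost is two fields on the bedside form and a few sentences in Sections 8, 9 and 16. Flatus times will be approximate, but errors of up to 4 h cost almost no power in the second model above. Separate fields also leave both definitions open to analysis.

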7 STUDY TIMELINES

The study duration is 24 months or until target accrual is reached. Subjects will be on study until they are discharged from the hospital. Subjects will be followed 30 days post discharge to note any complications or readmission. A post study questionnaire will be given to participants during one of their follow up visits which happen 2 weeks, 6 weeks, 3 months post discharge or over the phone if missed.

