11 RISKS TO SUBJECTS

Risk of fall is associated with mobility. This will be minimized with standard procedures including; patient risk of fall stratification, supervised patient mobility and using balance assessment programs.

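### Complications have three different scopes in the plan; if Section 8's surgery-related restriction governs, an unmasked judgement of cause could drop walking-related events more often in the intervention arm.

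*Combined protocol and SAP*

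**What the plan says.** All references are to the combined protocol and SAP.

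- **Section 8 (Study Endpoints)** lists, within the primary endpoint, "early discharge from the hospital and 30 days surgical related complications and readmissions". This is a restriction by cause. Section 8 does not say when the 30 days start.
- **Section 7 (Study Timelines)** says "Subjects will be followed 30 days post discharge to note any complications or readmission", and **Section 9 (Procedures Involved)** says "We will continue to follow them for 30 days post discharge to note any complications or readmission". Neither restricts by cause. Both tie this recording to the period after discharge.
- **Section 9, in hospital**, lists only gastro-intestinal and chest symptoms for assessment.
- **Section 16 (Statistical Plan)** says "The secondary objective is to evaluate the impact on post-surgical complications" and then "The complication status (present/absent) and grades will be summarized by group and compared using Fisher's exact test or the chi-square test, as appropriate". It states no filter by cause.
- **Section 9, tasks:** "The intervention arm participants will be asked to walk for minimum 30 minutes per day". Control patients are asked for one to two laps of the ward twice a day. Both arms get out of bed "under supervision and assistant of attending nurse in the floor if their clinical situation allowed". Patients who cannot complete the walking tasks are excluded and replaced.
- **Section 11 (Risks to Subjects)** names one risk: "Risk of fall is associated with mobility". **Section 14 (Safety Reporting)** is marked N/A.

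No section defines surgery-related, says who would judge it, or provides masked assessment or adjudication.

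**The concern.** Section 8 filters by cause, Sections 7 and 9 record everything after discharge, and the Section 16 wording can be read as timing alone. Nothing says which governs, so the choice could be made after the data are seen.

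The Section 8 filter is the one that can bias the comparison. It needs a judgement of cause for each event. The amount of walking is what distinguishes the arms, and it is also a rival explanation for some events. An assessor who knows the arm may, in good faith, put a fall down to walking and not to the operation. That explanation is available in both arms, but more often in the one that walks more. The filter could then remove events that the intervention itself caused.

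The Section 16 complication test is the only planned between-arm comparison in which such an effect could appear. An event removed there is compared nowhere else.

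**Working it through.** **1. The plan's own figure.** Section 16 states 80% power with 40 per group for a difference of 0.63 SD, two-sided alpha 0.05. This reproduces: 0.804 by the normal approximation and 0.795 by the noncentral t. It concerns change in mobility and says nothing about complications. The plan gives no complication rate and no power for that comparison, so every rate below is an assumption.

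**2. The scopes side by side.**

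| Section | Role | Cause filter | Period |
|---|---|---|---|
| 8 | Endpoint | Surgery-related only | 30 days, start not given |
| 7 and 9 | Recording after discharge | None | 30 days from discharge |
| 9 | Recording in hospital | None, but gastro-intestinal and chest symptoms only | To discharge |
| 16 | Analysis | None stated | Not given |

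Take a fall on the ward during a supervised walk. Under Section 8 it can be ruled out on cause. Under Section 16 read as timing, it counts. Under Section 9 it may not be recorded, because it happened before discharge and is neither a gastro-intestinal nor a chest symptom.

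**3. Effect of unequal removal when there is no true difference.** Assume 12 of 40 (30%) in each arm. If *a* intervention and *b* control patients are reclassified, the false benefit is [(12 − *b*) − (12 − *a*)]/40 = (*a* − *b*)/40.

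| Removed, intervention (*a*) | Removed, control (*b*) | Counts, control vs intervention | False benefit | Fisher p, two-sided |
|---|---|---|---|---|
| 2 | 0 | 12 vs 10 | 2/40 = 5 points | 0.80 |
| 3 | 0 | 12 vs 9 | 3/40 = 7.5 points | 0.61 |
| 4 | 0 | 12 vs 8 | 4/40 = 10 points | 0.44 |
| 4 | 2 | 10 vs 8 | 2/40 = 5 points | 0.79 |
| 2 | 2 | 10 vs 10 | 0 | 1.00 |

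The bias depends on the imbalance in removal. Equal removal gives none.

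**4. Effect on a real excess.** With 18 intervention and 8 control events, Fisher p = 0.031. Setting aside one intervention event (17 vs 8) gives 0.053, and two (16 vs 8) gives 0.087.

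**5. Operating characteristics, assumed rates.** Let control events follow Binomial(40, p_C) and counted intervention events follow Binomial(40, p_I(1 − r)), where r is the share removed in the intervention arm only. Fisher's two-sided test at 0.05 was enumerated exactly.

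- True rates 20% control and 40% intervention: power to show the excess is 40.8% at r = 0, 27.5% at r = 10% and 12.3% at r = 25%.
- Equal true rates of 20%, 30% or 40%: the chance of a significant false benefit is 1.4% to 1.5% at r = 0. At r = 25% it is 5.2%, 7.6% and 10.4% respectively.

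**The case against.** The strongest reply is that no filter appears in the analysis. Section 16 states no exclusion by cause, no section describes a step that classifies events by cause, and the Section 8 phrase may be loose drafting for postoperative. Recording more than the endpoint uses is not in itself a contradiction. This stands in part: if Section 16 governs and means timing, nothing is dropped. But the documents do not say so, and the narrower wording sits in the endpoint definition.

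A reader might infer that staff who know the arm will strip the harms of walking from the trial. The documents do not support that. Knowledge of the arm is inferred from visibly different, nurse-supervised tasks and the absence of masking text. The person who would classify events is not named. Control patients also walk, so walking is a possible cause in both arms and differs in amount. No walking task is described after discharge, so much of the follow-up is less exposed. The plan labels no comparison as one of harm.

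It is also fair to say that a wording change in Sections 8 and 16 would not be enough. Falls or other events during supervised walking would mostly occur in hospital, where recording covers only two symptom groups. A patient who cannot finish the walking may also leave under the replacement rule before any judgement of cause. Both points stand and are built into the fix.

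Finally, the magnitudes rest on assumed rates and mostly on one-sided removal. That is correct, and with equal removal the bias disappears.

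**Conclusion.** The concern holds as a conditional one. The inconsistency is in the current text: three scopes for one outcome, with no rule for choosing among them. If the Section 8 wording is applied, an undefined judgement of cause with no stated masking could remove walking-related events unequally and favour the intervention. Such events would then be missing from the only planned between-arm complication test.

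The size is unknown. With an assumed 12 of 40 per arm and one-sided removal of 2 to 4 intervention patients, the spurious benefit is 5 to 10 percentage points and not significant. It shrinks as control removals approach intervention removals. With few events, a borderline real excess could be lost by reclassifying a single patient, as the 18 vs 8 example shows. None of this shows that misclassification would occur; the case for change is that the plan permits it and a rule without a cause filter avoids it. The Section 16 sample size calculation is not affected.

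**What to change.** 1. In Sections 8 and 16, define the outcome identically: all complications and all readmissions, regardless of judged cause, from surgery through 30 days after discharge.
2. Apply it to every randomised patient, including those who cannot complete the walking tasks. State in Section 9 that replacing a patient does not remove that patient from this comparison.
3. In Section 9, widen in-hospital recording from gastro-intestinal and chest symptoms to any complication, taken from the inpatient record in the same way for both arms.
4. If a surgery-related subset is wanted, define it, name who judges it (preferably without knowledge of the arm), and report it as descriptive only.

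**Cost.** Wording in Sections 8, 9 and 16, abstraction of in-hospital complications, and continued follow-up of patients who stop the walking tasks. The stated power for mobility does not change. Some unrelated events will enter the count and add noise, expected to fall about equally on the two arms.
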